8.15.4 Reporting pregnancy

Pregnancy testing must be performed on all women of childbearing potential prior to dosing, and all the results of all pregnancy tests are to be recorded in the eCRF's. All women must have a negative pregnancy test to be enrolled into the study. If a pregnancy test turns positive after study drug treatment, the patient will be discontinued and protocol-required procedures for study discontinuation and follow-up must be performed. The subject will be followed to determine the outcome of the pregnancy. All women of childbearing potential should be instructed to contact the investigator if they suspect they might be pregnant (e.g. missed or late menstrual period) at any time during the study.

The investigator must notify the sponsor of any pregnancies in accordance with the SAE reporting procedures described in section 8.14.3. Note, while the pregnancy is not considered an AE or an SAE, any pregnancy complication or newborn complication will be reported as an AE or SAE if it meets the criteria. Follow-up information regarding the course of pregnancy, including perinatal and neonatal outcomes and, where applicable, offspring information must be reported on the Pregnancy Outcome eCRF.

8.15.5 Recording of Serious Adverse Events

All SAE information must be recorded on the SAE form provided by the Sponsor. Additional follow-up information (e.g., test results, autopsy, and discharge summary) must be obtained to supplement the SAE report form. A copy of all initial and follow-up reports must be filed with the subject's eCRF.

9.0 STATISTICAL CONSIDERATIONS

9.1 Sample Size Determination

A total of 75 subjects will be included in the study. All subjects will be treated with RZL-012. Each 15 subjects will be randomized into each of the treatment groups.

9.2 Analysis Data Sets

Subjects who receive study treatment will be included in the safety analyses.

9.3 Endpoints Analyses

All measured variables and derived parameters will be listed individually and, if appropriate, tabulated by descriptive statistics.

For categorical variables, summary tables will be provided giving sample size, absolute and relative frequency, and 95% confidence interval (CI) for proportions by study arm.

For continuous variables, summary tables will be provided giving sample size, arithmetic mean, standard deviation, coefficient of variations (CV%), median, minimum and maximum, and 95% CI for means of variables by study arm.

Primary endpoint and exploratory endpoints will be analyzed in descriptive manner.

The data will be analyzed using the SAS version 9.4 (SAS Institute, Cary North Carolina).

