	
4. RZL-012 and Celecoxib and cetirizine (200 mg Celecoxib BID and 10 mg cetirizine BID on Days 1, 2, 3, 4, 5 and 6)
 
5. RZL-012 + sling/pressure garment (until Day 6)
 
In the first stage of the study, 5 subjects will be randomized into each of the treatment groups. Study outcomes will be assessed up to one week thereafter to determine the need to modify additional study treatments. Subsequently up to 10 additional subjects will be randomized into each of the treatment groups for the second stage of the study.
 
For each subject, the study will consist of a screening period, baseline period in which subjects will receive a single treatment session of RZL-012 and a follow-up period. RZL-012 will be administered during a single treatment session via multiple injections into the submental area under the chin. Subjects will thereafter be monitored for safety and efficacy for at least 84 days.
 
Each subject will be treated with the same dose of RZL-012 :
 
• RZL-012 (concentration of injected solution 50 mg/mL RZL-012) of 7.5 mg/0.15 mL/injection point that results in a total dose/volume of 240±30mg mg/4.8±0.6 mL RZL-012, 
Each subject will receive additional study treatments in accordance with the treatment group to which the subject is randomized.
 
Screening Period:
 
Subjects will undergo screening within 28 days prior to being treated with RZL-012. During the screening period subjects will be assessed for study eligibility by evaluation of subjects' SMF using S-CAT , C-CAT, biochemistry blood tests, MRI, 2D photography. ECG will also be conducted during the screening visit. Following completion of study procedures (including MRI), subjects will be randomized in order for the PI to administer subjects with the Rx prescription, if appropriate (i.e., Celecoxib / cetirizine).
 
Day 1/Baseline:
 
At Baseline visit, subjects will be given with their randomized medication if appropriate. Subjects will receive a single multi-injection treatment of RZL-012 on Day 1. AEs will be recorded. Subjects will be asked about their pain levels using VAS. Additional medications/treatments, will be given according to its instructions for use.
 
Day 1-Day 84 Follow-Up Period
 
Subjects will return to the site for study visits on Days 2, 4, 7, 14, 21, 28, 56 and 84 for efficacy and safety assessments.
 
For subjects having unresolved AEs on Day 84, an unscheduled visit will be set 6-8 weeks after Day 84 to verify the resolution of the AE. On that visit, follow up of using photographs C-CAT and S-CAT will also be conducted.
 
Subjects will be advised to continue their regular diet and physical activity during the study.
 
Safety assessments include vital signs, ECG, AEs severity assessment, and treatment area evaluation. Treatment area evaluations including, but not limited to evaluation of edema, bruising, dysphasia, dysphonia, erythema, dyspigmentation, induration, numbness, pain, paresthesia, pruritus, skin ulceration and necrosis, injury to the marginal mandibular nerve, vascular and nerve injury and tissue damage to nearby vulnerable anatomic structures. Specifically, degree of swelling severity will be assessed as a function of time and in each visit Subjects will be asked about their pain levels using VAS. Pain at injection site will not

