8.15 Adverse Events and Serious Adverse Events

8.15.1 Collection of Adverse Events Data

An AE is any unfavorable and unintended sign, symptom, or disease temporally associated with the use of an investigational (medicinal) product (IP) or other protocol-imposed intervention, regardless of attribution. An AE may include intercurrent illnesses or injuries that represent an exacerbation (increase in frequency, severity, or specificity) of pre-existing conditions (e.g., worsening of asthma). A laboratory abnormality will be reported on the “Adverse Event” case

report forms only if it is associated with clinical sequelae or requires therapeutic intervention. Whenever possible, it is preferable to record a diagnosis as the AE term rather than a series of symptoms relating to a diagnosis. AEs will be coded according to the Medical Dictionary for Regulatory Activities (MedDRA) and graded for severity. In case the AE severity is changed from one severity grade to the another the date of AE start and AE end of the specific AE severity should be recorded.

The reporting period for AEs starts after dosing of study drug and will end at final study visit. If an AE remains unresolved at discharge, the subject will be followed, at the Investigator’s discretion, until resolution of the event or until the subject is deemed “lost to follow-up”. SAEs must be followed until resolution by the PI, even if this extends beyond the study-reporting period. Resolution is defined as the return to baseline status or stabilization of the condition with the expectation that it will remain chronic.

The Investigator will assess AEs for severity, relationship to IP, and as to whether the event meets one or more of the definitions of an SAE. The assessments will be recorded on the source documents and AE CRF, using the categories defined below.

Causality Category	Description
Unrelated	A clinical event, including laboratory test abnormality, with a temporal relationship to drug administration which makes a causal relationship improbable, and in which other drugs, chemicals or underlying disease provide plausible explanations. For the purpose of this protocol, the term unlikely will be considered not related to study medication and an “Adverse Event”.

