9.4 Safety

Safety data will be summarized by dose group and based on their initial dose level or treatment group (i.e., if a dose reduction occurs, they will be considered in their initial group). Descriptive statistics will be provided for actual values and change from baseline values for vital signs, blood parameters, ECG.

AE assessment and treatment area evaluation including, but not limited to evaluation of edema, pain, bruising, erythema, induration, numbness, paresthesia, tenderness, and pruritus. Pain in the injection site will be assessed by Visual Analog Scale (VAS) in each of the visits. Injection site pain will not be recorded as an AE.

The incidence and severity of AEs reported during the study and their relationship to study drug will be tabulated. AEs will be coded using MedDRA™ and will be presented by body system.

AEs related to nerve damage such as: paralysis, mandibular neuropathy, facial palsy will be AEs with special interest, i.e., the PI will write a detailed narrative on these specific AEs.

AE data will be listed individually and summarized by SOC and by PT within a system organ class.

Skin irritancy AEs related to the injection procedure will be evaluated for frequency, severity and duration by treatment group.

Laboratory tests and ECG results will be summarized in appropriate table.

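### The by-arm summary of skin irritancy AE duration defaults to an arithmetic mean, with no rule for AEs that have no end date, so a contrast on lasting reactions can be understated

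*Combined protocol and SAP*

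**What the plan says.** Section 9.4 plans a duration comparison for one class of event: "Skin irritancy AEs related to the injection procedure will be evaluated for frequency, severity and duration by treatment group". It names no estimator. Section 9.3 gives the general rule for continuous variables: "For continuous variables, summary tables will be provided giving sample size, arithmetic mean, standard deviation", continuing with "coefficient of variations (CV%), median, minimum and maximum, and 95% CI for means of variables by study arm". Nothing else in the plan covers duration.

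The protocol foresees events still open at the last scheduled visit. The synopsis states: "For subjects having unresolved AEs on Day 84, an unscheduled visit will be set 6-8 weeks after Day 84 to verify the resolution". Section 8.15.1 follows an AE unresolved at discharge, at the Investigator's discretion, "until resolution of the event or until the subject is deemed “lost to follow-up". The same section defines resolution to include stabilisation of a condition that is expected to stay chronic.

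The close of AE collection is given in two ways. The Safety Analysis row of the synopsis ends it on Day 84; Section 8.15.1 ends it at the final study visit. No section says whether an end date found at the extra visit enters the duration summary, or what is done with an AE that never receives one.

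**The concern.** A duration can be averaged only when both its dates are known. For an open AE there are two simple ways out: leave it out, or treat the last contact as its end. The first averages only the AEs that resolved in time. The second records a lower bound as if it were the duration. Both pull the mean down, and more so in the arm with more lasting events.

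The primary objective is to compare what the add-on treatments do for RZL-012-induced AEs, and duration is one of the few by-arm AE measures that Section 9.4 names. The analysis is descriptive, so no test is invalidated. But the descriptive contrast is the whole output, and any shrinkage passes straight into the reading of the trial.

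**Working it through.** **Figures in the plan.** The documents give no AE duration and no share of AEs unresolved at Day 84, so there is no duration figure to reproduce. The sample size is plain arithmetic: 5 arms × (5 + 10) = 75, or 15 per arm.

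**Inputs**
- Horizon without the extra visit: Day 1 to Day 84, c = 83 days.
- Horizon with it: 6 to 8 weeks later, c = 83 + 42 = 125 to 83 + 56 = 139 days.
- Durations (assumption): exponential with mean m, onset on Day 1, mean in the add-on arm half that of RZL-012 alone.

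**Formulas**
- Share unresolved at c: S = exp(−c/m).
- Mean of AEs resolved by c: m − c·S/(1 − S).
- Mean with open AEs cut at c: m·(1 − S).

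**Worked case, 60 v 30 days, c = 83**
- S = exp(−83/60) = 0.251 and exp(−83/30) = 0.063. With 15 AEs per arm (one per subject, an assumption), that is about 3.8 v 0.9 open AEs.
- Resolved only: 60 − 83 × 0.251/0.749 = 32.2; 30 − 83 × 0.063/0.937 = 24.4. Difference 7.8, against a true 30.
- Cut at Day 84: 60 × 0.749 = 45.0; 30 × 0.937 = 28.1. Difference 16.8 from unrounded values.

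**Range of assumed durations (difference between arms, days)**

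| True means | True difference | Unresolved at Day 84 | Resolved by Day 84 only | Resolved by extra visit only (c = 125 to 139) | Cut at Day 84 |
|---|---|---|---|---|---|
| 14 v 7 | 7 | 0.3% v 0% | 6.8 | 7.0 | 7.0 |
| 30 v 15 | 15 | 6.3% v 0.4% | 9.8 | 13.1 to 13.6 | 13.2 |
| 40 v 20 | 20 | 12.6% v 1.6% | 9.4 | 14.5 to 15.7 | 15.3 |
| 60 v 30 | 30 | 25.1% v 6.3% | 7.8 | 14.2 to 16.2 | 16.8 |
| 90 v 45 | 45 | 39.8% v 15.8% | 5.8 | 11.8 to 13.9 | 16.3 |

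**Effect only on persistence.** Suppose 20% v 5% of AEs never resolve and the rest have mean 20 days in both arms. The resolved-only means at Day 84 are then identical, 18.7 v 18.7. The means restricted to Day 84 are 0.20 × 83 + 0.80 × 19.7 = 32.3 and 0.05 × 83 + 0.95 × 19.7 = 22.9 days (19.685 unrounded). This is the extreme case.

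**What a censored analysis recovers.** In simulation with 15 AEs per arm, cut at Day 84, the typical Kaplan-Meier medians are 41.5 v 20.6 days for 60 v 30 (true medians 41.6 v 20.8) and 62.8 v 31.3 for 90 v 45 (true 62.4 v 31.2).

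**The case against.** The strongest reply is that a reader might infer from Section 9.3 that the plan drops the longest AEs from the mean and so hides any benefit on lasting reactions. The documents do not say that. No text excludes open AEs, and cutting them at last contact is equally open. That reply stands, but cutting also understates the difference (16.8 of 30 days in the worked case), so the point does not depend on which route is taken.

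Other parts of the reply also stand:
- Duration is planned for skin irritancy AEs only. Wider use would be a new analysis, not a correction.
- The extra visit should supply some of the missing end dates. It roughly halves the loss for 40 v 20 days (14.5 to 15.7 of 20, against 9.4). The Day 84 close of collection in the synopsis leaves the use of those dates uncertain.
- Because a stable chronic condition can count as resolved, the never-resolving case is weaker than it looks.
- The fibrosis that Scientific Background describes at 12 weeks is pig histology, part of a healing process. It does not show that human reactions last to Day 84.
- Section 9.3 also reports the median, and Section 9.4 lists AEs individually. But a median of resolved AEs alone has the same selection problem, and listings do not compare arms.
- The mechanism is selection on, or truncation of, open events. It is not informative censoring, which would undermine Kaplan-Meier as well.

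None of this makes an arithmetic mean suitable for durations with open ends.

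**Conclusion.** The point holds for the skin irritancy duration summary. The plan pairs a default arithmetic mean and CI with events that it expects may be open at the end, and gives no rule for them. The direction is clear when one arm has more lasting reactions: its duration is understated most, and the contrast shrinks.

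The size is not known. Under the exponential assumption it is negligible if reactions clear in about two weeks. It is large if about a quarter of AEs in the RZL-012-alone arm are open at Day 84, where 7.8 of 30 days would show, or 14.2 to 16.2 with end dates from the extra visit. Complete loss of the contrast needs an effect confined to persistence and is not the expected case. The change is worth making because it is cheap and the descriptive contrast is all that the trial will report.

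**What to change.** In Section 9.4, for AE duration:
- Replace the arithmetic mean and its CI with a Kaplan-Meier summary of time from onset to resolution per arm, with unresolved AEs censored at last contact.
- Report the median, the number and percentage unresolved at Days 28, 56 and 84, and the restricted mean to Day 84 with 95% CI. If nobody is lost before Day 84, the restricted mean has the same value as a mean cut there. What it adds is an explicit horizon, so that it is not read as mean duration, and proper handling of earlier losses.
- State whether end dates from the visit after Day 84 are used, and reconcile the synopsis with Section 8.15.1 on when AE collection ends.
- Report resolution by chronic stabilisation separately from return to baseline.

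Applying the same summary to swelling, induration and numbness is optional.

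The cost is a few lines in Section 9.4 and a small amount of extra programming with a standard procedure. The main inputs are AE start and end dates, which an evaluation of duration needs in any case.

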9.4 Safety

Safety data will be summarized by dose group and based on their initial dose level or treatment group (i.e., if a dose reduction occurs, they will be considered in their initial group). Descriptive statistics will be provided for actual values and change from baseline values for vital signs, blood parameters, ECG.

AE assessment and treatment area evaluation including, but not limited to evaluation of edema, pain, bruising, erythema, induration, numbness, paresthesia, tenderness, and pruritus. Pain in the injection site will be assessed by Visual Analog Scale (VAS) in each of the visits. Injection site pain will not be recorded as an AE.

The incidence and severity of AEs reported during the study and their relationship to study drug will be tabulated. AEs will be coded using MedDRA™ and will be presented by body system.

AEs related to nerve damage such as: paralysis, mandibular neuropathy, facial palsy will be AEs with special interest, i.e., the PI will write a detailed narrative on these specific AEs.

AE data will be listed individually and summarized by SOC and by PT within a system organ class.

Skin irritancy AEs related to the injection procedure will be evaluated for frequency, severity and duration by treatment group.

Laboratory tests and ECG results will be summarized in appropriate table.

10.0 DATA COLLECTION, STUDY MONITORING, AND DATA DISCLOSURE

10.1 Data Collection and Reporting

An eCRF will be completed for each subject who receives at least one dose of study drug. All entries on the eCRF must be supported by original source documentation (e.g., laboratory reports, medical records) maintained at the investigational site.

The Investigator will make all safety assessments (AEs and vital signs) on an ongoing basis. The Investigator is required to review all entries on the eCRF and sign at appropriate time intervals.

10.2 Study Monitoring

All aspects of the study will be monitored carefully by the Sponsor's designees with respect to current Good Clinical Practice (GCP) and Standard Operating Procedures (SOP) for compliance with applicable government regulations. It is the responsibility of the Investigator to provide all study records, including eCRFs, source documents, etc., for review and source document verification by the clinical monitor.

All eCRFs will be 100% source verified against corresponding source documentation (e.g., office and clinical laboratory records) for each subject. Clinical monitors will evaluate periodically the progress of the study, including the verification of appropriate consent form procedures, review of drug accountability and preparation procedures, adherence to dosing procedures, and the verification of the accuracy and completeness of eCRFs. Clinical monitors will also ensure that all protocol requirements, applicable FDA regulations, other requirements, and Investigator's obligations are being fulfilled.

10.3 Audit and Inspection

The sponsor or representative may conduct audits at the trial site(s). Audits will include, but are not limited to protocol compliance, drug supply, presence of required documents, the informed consent process, and comparison of eCRFs with source documents. The investigator agrees to participate with audits conducted at a reasonable time in a reasonable manner.

Regulatory authorities worldwide may inspect the trial site during or after the trial. The investigator should contact the sponsor immediately if this occurs and must fully cooperate with the inspections conducted at a reasonable time in a reasonable manner.

10.4 Deviation from Clinical Trial Protocol

Deviations from the protocol are to be avoided. If a deviation occurs, the Investigator must promptly report the deviation to the study monitor.

The Investigator (or designee) will record any failure to follow the protocol because of any other medical unavoidable reason to avoid the subject's urgent risk and record a document as soon as possible stating this and the reason. It must be submitted to the sponsor and the director of the study site.

10.5 Retention of Records

The Investigator must retain all study records required by Raziel and by the applicable regulations in a secure and safe facility. The Investigator must notify Raziel of any change in the location, disposition or custody of the study files. The Investigator /institution must take measures to prevent accidental or premature destruction of essential documents, that is, documents that permit evaluation of the conduct of a study and the quality of the data produced, including paper copies of study records (e.g., subject charts) as well as any original source documents that are electronic as required by applicable regulatory requirements.

All study records must be retained until whichever is the later day in the following: (1) At least the date of approval for the drug or (2) the date when 3 years have passed since the discontinuation or completion of the study. No records relating to this study should be disposed of without the written approval of Raziel. It is the responsibility of Raziel to inform the Investigator/institution as to when these documents no longer need to be retained.

10.6 Data Disclosure and Subject Confidentiality

Subject medical information and video recordings obtained as a result of this study is considered confidential and used only for study evaluation purposes. Disclosure to third parties other than those noted below is prohibited. All reports and communications relating to subjects in this study will identify each subject only by number. Medical information resulting from a subject's participation in this study may be given to the subject's personal physician or to the appropriate medical personnel responsible for the subject's welfare. Data generated as a result of this study are to be available for inspection on request by FDA or other government regulatory agency auditors, the Sponsor clinical monitor (or designee), and the IRB/EC.

All laboratory specimens, evaluation forms, reports, and other records that leave the site will be identified by a coded number to maintain subject confidentiality. All records will be kept in a locked and secured area. All computer entry and networking programs will be identifiable only by coded numbers. Clinical information will not be released without written permission from the subject, except as necessary for monitoring by the IRB, the FDA, or other government authorities where the clinical data will be used for new drug registration, or the study Sponsor.

Any information, inventions, or discoveries (whether patentable or not), innovations, suggestions, ideas, and reports, made or developed by the Investigator(s) as a result of conducting this study shall be promptly disclosed to the Sponsor and shall be the sole property of the Sponsor. The Investigator agrees, upon the Sponsor's request and at the Sponsor's expense, to execute such documents and to take such other actions, as the Sponsor deems necessary or appropriate, to obtain patents in the Sponsor's name covering any of the foregoing.

The results of this study will be published under the direction of the Sponsor. Results will not be published without prior review and approval by the Sponsor and Study Investigator.

